4.5.2 CFZ533 specific risks

CD40 ligation is linked to the functional activity of antigen presentation, as well as T cell priming, B cell differentiation, antibody production and immune memory. Administration of CFZ533 is expected to result in general immune suppression with a decreased capacity to mount a response to novel immunogens, including those of bacterial, viral, fungal and parasitic origin. However, although the ability to mount a primary immune response will be affected by CFZ533, the memory B cell and plasma cell repertoire should remain intact and protective. In addition, subjects will have adequate preformed serum antibody to maintain protective humoral response for extended periods of time. Infections in patients treated with CFZ533 in clinical trials involving healthy volunteers or patients with RA or other rheumatic diseases are overall mild-to-moderate in severity.

Thrombosis. Thromboembolic events have been reported in clinical trials with CD154 (CD40 ligand) blocking antibodies, but not with CD40 blocking antibodies. The risk of thromboembolic events with CFZ533 is considered minimal. CCI

Investigation in human FcγR transgenic mice revealed the absence of thromboembolic activity of a blocking, non-depleting anti-CD40 mAb, whereas anti-CD154 mAb caused thrombocytopenia and thrombi formation. *In vitro* whole blood aggregation assays also demonstrated platelet activation liabilities of anti-CD154 but not anti-CD40 mAbs. Clinical data for CFZ533 available to date do not suggest an increased risk of thromboembolism. Furthermore, there have been no reports of thromboembolic complications with other anti-CD40 antibodies, including dapirolizumab, lucatumumab or ASKP1240 (anti-CD40 antibody by Astellas Pharma). Although risk of thromboembolism is theoretical, hematologic and coagulation parameters will be monitored in the current study. Furthermore, patients with conditions such as anti-phospholipid syndrome who are at a higher risk for thromboembolism will be excluded from the CFZ533 arm unless they are receiving anti-thrombotic prophylaxis.

CCI

Please refer to Section 7 in the CFZ533 IB current edition for further information, further details on the above specific risks and other potential adverse effects of the compound.

4.5.3 Benefits of VAY736 and CFZ533

There is a large, unmet need in SLE for new immunosuppressive treatments with less severe adverse effects. The expected benefit profiles in patients with SLE for VAY736 and CFZ533 are anticipated to provide reductions in disease activity and improved quality of life along with reduced toxicities compared to existing treatments. Additionally, these clinical benefits from VAY736 and from CFZ533 are expected to reduce dependence on chronic corticosteroid use and prevent long term organ damage.

4.5.4 Blood sample volume

A total blood volume of approximately 790 mL will be collected over the course of the initial 13-month screening / treatment phase up to Study Week 53. Approximately 205 mL of additional blood will be collected during the 4-month Follow-up period (Study Week 57 to Week 69). Thus, for the entire study from Screening until the Week 69 visit, an overall total blood volume of approximately 995 mL over 18 months will be collected.

For patients tested positive for HepBc Ab, an additional overall blood volume of approximately 140 mL will be taken up to V399 (Month 18) for both Cohorts. Monthly hepatitis B monitoring will be continued after V399 to V400 (12 months after last treatment) for all patients in Cohort 1 who tested positive for HepBc Ab. For patients who do not achieve B cell recovery, testing will continue at every visit (8 mL at each visit) until EoS visit Cohort 1.

For patients randomized to the CFZ533 cohort, an additional blood volume of approximately 115 mL from Baseline until Week 69 will be collected for local CMV monitoring.

Patients in Cohort 1 (VAY736) who do not achieve B cell recovery criteria at the Week 69 visit will continue the study and enter into a secondary Follow-Up period starting after the Week 69 visit has been completed. At each of the visits in the secondary Follow-Up period, approximately 15 mL of blood (plus 8 mL if HepB monitoring is required) will be collected to monitor safety laboratory and B cell recovery. At EoS visit for Cohort 1 approximately 60 mL of blood will be collected. Since each patient in Cohort 1 (VAY736) will have an individual follow-up time to achieve B cell recovery criteria, a total blood volume taken throughout the study cannot be given. Additional samples may be required for safety monitoring or repeat measures.

Timings of blood sample collection are outlined in the [Assessment Schedule](#).

A summary blood log is provided in the Site Operations Manual (SOM). Instructions for all sample collection, processing, storage and shipment information is also available in the SOM and central laboratory manual.

4.6 Rationale for Public Health Emergency mitigation procedures

During a public health emergency as declared by local or regional authorities e.g., pandemic, epidemic or natural disaster, mitigation procedures to ensure participant safety and trial integrity are listed in relevant sections. Notification of the public health emergency should be discussed

with Novartis prior to implementation of mitigation procedures, which should be then permitted/approved by local or regional Health Authorities and Ethics Committees as appropriate.

5 Population

The patient population will be comprised of adult male and female patients with active SLE.

The investigator must ensure that all patients being considered for the study meet the following eligibility criteria. No additional criteria should be applied by the investigator, in order that the study population will be representative of all eligible patients.

Patient selection is to be established by checking through all eligibility criteria at screening. A relevant record (e.g., checklist) of the eligibility criteria must be stored with the source documentation at the study site.

Deviation from **any** entry criterion excludes a subject from enrollment into the study.

Patient re-screening will be allowed in the study.

5.1 Inclusion criteria

Subjects eligible for inclusion in this study must meet **all** of the following criteria:

1. Written informed consent must be obtained before any assessment is performed
2. Male and female patients 18 to 75 years of age
3. Fulfill ≥ 4 of the 11 American College of Rheumatology 1997 classification criteria for SLE ([Hochberg 1997](#); [Tan et al 1982](#)) at screening
4. Patient diagnosed with SLE for at least 6 months prior to screening
5. Elevated serum titers at screening of ANA ($\geq 1:80$) of a pattern consistent with an SLE diagnosis, including at a minimum either anti-double stranded DNA (anti-ds DNA) or anti-Ro (SSA) or anti-La (SSB) or anti-nuclear ribonucleoprotein (anti-RNP) or anti-Smith (anti-Sm)
6. Currently receiving corticosteroids and/or anti-malarial and/or thalidomide treatment and/or another DMARD **CCI**

7. SLEDAI-2K score of ≥ 6 ([Gladman et al 2002](#)) at screening

8. BILAG-2004 score at screening of:
 - at least one “A” in either the mucocutaneous domain or in the musculoskeletal domain,
OR
 - one “B” in either the mucocutaneous or musculoskeletal domain AND at least one “A” or “B” in a second domain ([Isenberg et al 2005](#), [Isenberg et al 2011](#), [Yee et al 2006](#), [Yee et al 2010](#))
9. Able to communicate well with the investigator, to understand and comply with the requirements of the study
10. Weigh at least 40 kg at screening

5.2 Exclusion criteria

Subjects meeting any of the following criteria are not eligible for inclusion in this study.

1. **Cohort 2 (CFZ533/Placebo) only:** Patients who are at significant risk for thromboembolic events based on the following:
 - History of either thrombosis or 3 or more spontaneous abortions
 - Presence of lupus anticoagulant or significantly prolonged activated partial thromboplastin time (aPTT) consistent with co-existent anti-phospholipid syndrome and without concurrent prophylactic treatment with aspirin or anticoagulants as per local standard of care
2. History of receiving prior to screening:
 - Within 12 weeks: high dose corticosteroids (i.e., ≥ 500 mg Solumedrol or equivalent), calcineurin inhibitors, or other oral DMARD except as listed in inclusion criterion 6
 - Within 24 weeks: cyclophosphamide or biologics such as intravenous Ig, plasmapheresis, anti-TNF- α mAb, CTLA4-Fc Ig (abatacept) or BAFF-targeting agents (e.g., belimumab)
 - Any B cell depleting therapies (e.g., anti-CD20 mAb, anti-CD22 mAb, anti-CD52 mAb) or TACI-Ig (atacept) administered within 52 weeks prior to screening, and a B cell count < 50 cells/ μ L at the time of screening.
3. Evidence of past exposure to tuberculosis (TB) as assessed by Quantiferon testing at screening. Patients with history of latent TB infection may be eligible if they have received and completed appropriate anti-TB treatment according to national guidelines
4. Presence of human immunodeficiency virus (HIV) infection at screening
5. Any of the following abnormal laboratory values:
 - Platelets $< 50,000/\text{mm}^3$ ($< 50 \times 10^9/\text{L}$)
 - Hemoglobin (Hgb) < 8.0 g/dL (< 5 mmol/L)
 - Neutrophil count ($< 1,000/\text{mm}^3$) ($< 1.0 \times 10^9/\text{L}$)
6. Have donated blood or experienced a loss of blood > 400 mL within 3 months prior study entry, or longer if required by local regulations
7. Severe organ dysfunction or life-threatening disease

8. Presence of severe lupus kidney disease as defined by proteinuria above 6 g/day or equivalent using spot urine protein creatinine ratio, or serum creatinine greater than 2.5 mg/dL (221.05 µmol/L), or requiring immune suppressive induction or maintenance treatment exceeding protocol defined limits
 9. Active viral, bacterial or other infections at the time of screening or enrollment, or history of recurrent clinically significant infection or of recurrent bacterial infections with encapsulated organisms. CCI
[REDACTED]
[REDACTED]
 10. Receipt of live/attenuated vaccine within a 2-month period before first dosing
 11. Uncontrolled, co-existing serious disease, e.g., uncontrolled hypertension, heart failure, type I diabetes, thyroid disease within 3 months prior to first dosing, or significant, unresolved illness within 2 weeks prior to first dosing
 12. History of hypersensitivity to drugs of similar chemical class (e.g., IgG biologics) CCI
[REDACTED]
[REDACTED]
 13. History of non-compliance with medical regimens or considered potentially unreliable
 14. Use of other investigational drugs at the time of enrollment, or within 5 half-lives of enrollment, or until the expected PD effect has returned to baseline, whichever is longer; or longer if required by local regulations.
 15. Chronic infection with hepatitis B (HBV) or hepatitis C (HCV). A positive HBV surface antigen (HBsAg) test excludes a subject. HBsAg negative patients who are HepBc Ab positive are also excluded, except if both of the 2 following criteria are met: i) HBV DNA is negative, ii) Hepatitis B monitoring is implemented (HBsAg and HBV DNA tested on a monthly basis). CCI
[REDACTED]
[REDACTED]
- Subjects with a positive HCV antibody test should have HCV RNA levels measured. Subjects with positive (detectable) HCV RNA should be excluded.
16. History of malignancy of any organ system (other than localized basal cell carcinoma or squamous cell carcinoma of the skin or *in-situ* cervical cancer), treated or untreated, within the past 5 years, regardless of whether there is evidence of local recurrence or metastases.
 17. Pregnant or nursing (lactating) women.
 18. Women of child-bearing potential, defined as all women physiologically capable of becoming pregnant, **unless** they are using highly effective (for Cohort 1

VAY736/Placebo) or effective (for Cohort 2 CFZ533/Placebo) methods of contraception during dosing and for 6 months (for Cohort 1 VAY736/Placebo) or 14 weeks (for Cohort 2 CFZ533/Placebo) after stopping of investigational drug (or longer if required by concomitant medications).

CCI

CCI

19. Any surgical, medical, psychiatric or additional physical condition that the Investigator feels may potentially jeopardize the patient in case of participation in this study

20. Subjects who are committed to an institution by way of official or judicial order

No additional exclusions may be applied by the investigator, in order to ensure that the study population will be representative of all eligible subjects

6 Treatment

6.1 Study treatment

Details on the requirements for storage and management of study treatment, and instructions to be followed for subject numbering, prescribing/dispensing and taking study treatment are outlined in the SOM and the Pharmacy Manual.

6.1.1 Investigational and control drugs

Table 6-1 Investigational and control drug

Investigational/ Control Drug (Name and Strength)	Pharmaceutical Dosage Form	Route of Administration
CCI		

Clinical supplies are to be dispensed only in accordance with the specified study procedures.

A pharmacist or authorized designee is required to prepare the study drug. Instructions for storage and handling of study medication vials and preparation of infusion solution are described in the Pharmacy Manual (which is provided as a separate document).

6.1.2 Additional study treatments

CCI

6.1.3 Treatment arms/group

6.2 Other treatment(s)

6.2.1 Concomitant therapy

Permitted standard-of-care co-medications include oral CS and/or an anti-malarial agent (e.g., hydroxychloroquine) and/or thalidomide and/or one of the listed DMARDs: (see Inclusion criteria [Section 5.1](#)).

Table 6-2 Allowed concomitant medications

Medication	Condition
Ad hoc use of oral analgesics (NSAIDs, acetylsalicylic acid, paracetamol)	All use must be recorded in the concomitant medications / significant non-drug therapies
Corticosteroids	If CS is patient's single, SoC medication, an oral dose ≤ 30 mg/d ≥ 8 weeks prior randomization and stable dose for ≥ 2 weeks prior to randomization If CS is not patient's single SoC medication, an oral, stable dose of ≤ 30 mg/d for ≥ 2 weeks prior to randomization

CCI	
	Maintain baseline CS dosing from Study Week 1 to Week 5
Anti-malarials	Anti-malarial drugs (i.e., hydroxychloroquine, chloroquine, quinacrine) and/or thalidomide at stable dosing ≥ 8 weeks prior screening and remaining stable throughout blinded treatment period. Substitution between anti-malarial drugs is permitted if equivalent dosing is maintained.
DMARDs	Methotrexate or an imidazole derivative (e.g., azathioprine, mizoribine) or a mycophenolic acid derivative (e.g., mycophenolate mofetil) if at stable dosing ≥ 8 weeks prior to randomization and remaining stable throughout blinded treatment period.

Medication	Condition
	Any DMARDs that will be discontinued by the patient prior to study entry will require a minimum wash-out period of 4 weeks (methotrexate requires 8 weeks) or 5 half-lives, whichever is longer, unless noted otherwise in the protocol

Each concomitant drug must be individually assessed against all exclusion criteria/prohibited medication. If in doubt, the investigator should contact the Novartis medical monitor before randomizing a subject or allowing a new medication to be started. If the subject is already enrolled, contact Novartis/sponsor to determine if the subject should continue participation in the study.

All medications, procedures and significant non-drug therapies (including physical therapy and blood transfusions) administered after the subject was enrolled into the study must be recorded in the concomitant medications / significant non-drug therapies

6.2.2 Permitted concomitant therapy requiring action (guided CS tapering)

Corticosteroids. Patients on stable, maintenance dosing of oral corticosteroids (≤ 30 mg/day prednisone or equivalent) prior to randomization should continue this dosing level until Week 5. From Week 5 visit onwards, patients will undergo a guided CS dose reduction from baseline levels according to the following schedule:

- Achieve by Week 17 a prednisone dose or equivalent of ≤ 5 mg/day or less than CS dose at Baseline, whichever dose is lower.
- Any remaining corticosteroid dosing at Week 17 should subsequently be kept stable up to the Week 29 visit.
- Patients who are unable to reach these reduced CS dose level goals by week 17 or maintain these achieved CS dose levels through to Week 29 will be considered a non-responder for primary endpoint.
- Limited adjustments in CS dosing after Week 17 are provided (see [Section 6.2.4](#) Rescue medication and [Table 6-3](#) Prohibited medication).
- Further adjustments of corticosteroids and of other DMARD co-medications may take place during the open label period after Week 29 according to PI discretion.

6.2.3 Prohibited medication

Use of the treatments displayed in the below [Table 6-3](#) are not allowed after the start of the study.

Table 6-3 Prohibited medication

Medication	Prohibition period	Action taken
Other immune suppressive agents and biologics: 
 • Calcineurin inhibitors • Cyclophosphamide, intravenous Ig, plasmapheresis, anti-TNF-α mAb, CTLA4-Fc Ig (abatacept) or BAFF targeting agents (e.g., belimumab) • Any B cell depleting therapies (e.g., anti-CD20 mAb, anti-CD22 mAb, anti-CD52 mAb), atacicept, (TACI-Ig) 	Throughout treatment period through EoS	Withdrawal may be required on a case-by-case basis
• Total CS >30 mg/d prednisone or equivalent	Throughout treatment period through Week 29	Designated non-responder for primary endpoint
• Changes in CS dose	Within 2 weeks of Study Visit Week 29	Designated non-responder for primary endpoint
• Other experimental therapies	Throughout treatment period through to EoS	Withdrawal may be required on a case-by-case basis
• Live/ attenuated vaccines	
 • For Cohort 1 (VAY736): Throughout treatment period and follow up period up to 2 years after the EoT or until achieving B cell recovery (whichever occurs earlier) • For Cohort 2 (CFZ533): Throughout treatment period and up to 14 weeks after last CFZ533 dosing 	Study treatment discontinuation; patient should remain in study and follow visit schedule for safety monitoring until achieving EoS visit for their respective cohorts

6.2.4 Rescue medication

Corticosteroids may be administered to patients for SLE clinical disease flares after enrollment into this study as determined necessary by the responsible PI. However, patients receiving increased CS dose will be considered non-responders for primary study endpoint if any of following criteria was met:

- total daily CS dose is >30 mg/d prednisone or equivalent, or
- increased daily CS dose is administered >2 days within a 4-week treatment cycle from Week 17 to Week 29, or
- daily CS dose is increased within 2 weeks of Study Visit Week 29.

Where acute corticosteroid administration occurs for purposes other than the treatment of SLE disease activity, such as short-acting hydrocortisone dosed peri-operatively in patients with suppressed hypothalamic-pituitary-adrenal axis, patient responder status will be discussed on a case-by-case basis.

All Concomitant Medications as well as their dose changes must be recorded in the eCRF.

6.3 Subject numbering, treatment assignment, randomization

6.3.1 Subject numbering

The subject number will be assigned through the eCRF capture system to a patient at the screening visit and remains the unique identifier for the patient throughout the study. For more detailed information on subject numbering, please see 'Subject numbering' section in the Site Operations Manual.

6.3.2 Treatment assignment, randomization

Randomization has to be performed via the IRT system at the Baseline visit at the latest. All eligible participants will be randomized to one of the available treatment arms using the IRT system. The Investigator or his/her delegate will contact the IRT system after confirming that the participant satisfies all the inclusion/exclusion criteria. The IRT system will specify a unique medication number for the package of investigational drug to the participant. The randomization number will not be communicated to the requester.

The randomization scheme for participants will be reviewed and approved by a member of the Novartis Randomization Office.

If study participants are only eligible for VAY736 Cohort (i.e., meeting exclusion criterion 1), they will be randomized to either active arm or placebo arm of Cohort 1. Otherwise, the participants will be randomized to one of four treatment arms of two cohorts.

Randomization will be stratified by ENA status (positive vs. negative) and SLEDAI-2K <10, ≥10 status at Baseline, based on screening results, in order to remove any possible confounding impact on treatment effects.

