
 To evaluate the immunogenicity of multiple doses of VAY736 (s.c.) or CFZ533 (i.v.) in SLE patients 	
 Anti-VAY736 (Cohort 1) or anti-CFZ533 (Cohort 2) antibodies and incidence of ADA-positive patients

 To evaluate the pharmacodynamics (PD; rate, extent and duration of target engagement) of multiple doses of CFZ533 in SLE patients 	
 PD Cohort 2 (CFZ533): total soluble CD40 in plasma

Objective(s)	Endpoint(s)
Exploratory objective(s)	Endpoint(s) for exploratory objective(s)

Objective(s)	Endpoint(s)
CCI	

3 Study design

This is a randomized, patient- and investigator-blind, placebo-controlled, parallel-group, non-confirmatory study to assess the safety, tolerability, pharmacokinetics, immunogenicity, pharmacodynamics and preliminary clinical efficacy of multiple doses of VAY736 or of CFZ533 in patients with active SLE (see [Figure 3-1](#)).

Figure 3-1 Study design

Key study design features are as follows:

- Patient randomization into one of two treatment cohorts (VAY736 or CFZ533) and to either active or placebo
- Seven-month, placebo-controlled, blinded treatment
- Guided corticosteroid taper from Study Week 5 to Study Week 17
- A 5-month, open label treatment followed by a final outcomes assessment
- Four-month follow up for safety/PK/PD, with additional follow up for VAY736-treated patients until B cell recovery criteria are met, or up to 2 years after EoT whichever occurs earlier.

Screening and randomization

The study will randomize approximately 120 patients to test two active treatments against their matching placebo in parallel cohorts. After a 28-day screening period, eligible patients will be enrolled and stratified according to serum extractable nuclear antigens (ENA) status (positive

or negative) and baseline SLEDAI-2K score (<10 , ≥ 10). At the baseline visit, patients who are eligible for both cohorts will be randomly assigned to one of the four treatment arms. Patients who are eligible for only one cohort will be randomly assigned to either of the two treatment arms in that cohort. Randomization across the cohorts will be implemented via central randomization aiming for randomization ratio of 1:1:1:1.

Blinded treatment phase

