Hypogammaglobulinemia. In patients treated with VAY736, a trend toward reduction in IgM levels was observed with VAY736 in pSS patients and in RA patients; a finding consistent with reported experiences with other B cell depleting agents targeting CD20 such as rituximab (Marco et al 2014) and ocrelizumab. In the Ph2b study (CVAY736A2201) in pSS patients. For IgG, the proportion of patients below normal reference range at any time was low (2.1% in 4/188 patients) and there were no serious infections reported in these 4 patients. From this completed study, the observations of sustained IgG below normal reference range ≥ 12 weeks is low (1.1%, 2/187) (refer to IB). There were no disseminated infections with opportunistic pathogens reported from this completed study in patients treated with VAY736. Patients enrolled into the VAY736 cohort will have IgG and IgM levels monitored regularly during the study and follow up periods.

In humans, transient peripheral B cell depletion and lymphocytopenia have been reported in infants born to mothers exposed to anti-CD20 antibodies during pregnancy. The potential duration of B cell depletion in infants following maternal exposure to VAY736 in utero, and the impact of B cell depletion on the safety and effectiveness of vaccines, are both unknown. Women of child-bearing potential should be informed that taking the study treatment may involve unknown risks to the fetus if pregnancy were to occur during the study, and then should agree that in order to participate in the study, they must adhere to the contraception requirements required during the period of study treatment administration and the period after discontinuation of study drug as outlined in the protocol's exclusion criteria.

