8.4.4 Other safety evaluations

Quantiferon test

Both VAY736 and CFZ533 suppress the immune system and thus have potential for increasing susceptibility to mycobacterial infection. To identify patients exposed to *Mycobacterium tuberculosis* (MTb), a QuantiFeron test will be performed and read at screening (or within 6 months prior to randomization). Test may be repeated if test result is not unambiguous. A positive QuantiFeron test at screening will exclude the subjects from participation in the study.

T-SPOT or other types of ELISPOT assays based on interferon-gamma release may also be used for MTb diagnosis as per local practice.

Precautions against TB should be handled according to the best medical practice consistent to the local standards in each country with prior consultation with Novartis. Patients requiring administration of antibiotics against latent MTb infection should complete their treatment and should be considered cured prior to being re-considered for entry into this study (consultation with Novartis must occur before allowing the patient to enter the study).

Results will be available as source data and will not be recorded within the eCRF.

Hepatitis, HIV and CMV

Hepatitis

The immune suppressive effects of VAY736 and CFZ533 may exacerbate disease in patients with active viral hepatitis. All subjects will be screened for HBsAg and for HepBc Ab.

Table 8-3 Hepatitis screening

HBsAg	HepBc Ab	HBV DNA	Eligible	Comment
-	-	-	Yes	
-	+	-	Yes	Cohort 1 (VAY736/Placebo): monitoring required, prophylactic anti-viral treatment Cohort 2 (CFZ533/Placebo): monitoring only required
-	+	+	No	
+	+	+	No	

In case of HepBc Ab positivity:

- **Cohort 1 (VAY736/Placebo):** HBsAg negative patients who are HepBc Ab positive are also excluded except if all 3 following criteria are met: i) HBV DNA is negative, ii) prophylactic anti-viral treatment (e.g., lamivudine or entecavir) initiated latest on day 1 and continued until 12 months after last treatment. and iii) hepatitis B monitoring at study is implemented (HBsAg and HBV DNA) at study visits until EoS. In case of sero-conversion (i.e., if either HBsAg or HBV DNA turn positive), second line anti-viral treatments (e.g., tenofovir) will be initiated.

If Hepatitis B prophylaxis antiviral treatment is not recommended as per local guidelines for patients who are HepBc Ab positive and HBV DNA negative, ONLY HBsAg and HepBc Ab negative patients must be enrolled in the study

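### Protocol 6.3.2 contradicts Section 3 and SAP 1.4 on how a patient eligible only for the CFZ533 cohort is randomised

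*Protocol*

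**What the plan says.** Three places state the allocation rule.

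- **Protocol Section 3** (Screening and randomization) is symmetric. Its four-arm rule is that "patients who are eligible for both cohorts will be randomly assigned to one of the four treatment arms". For the remaining patients the rule reads: "Patients who are eligible for only one cohort will be randomly assigned to either of the two treatment arms in that cohort".
- **SAP 1.4** repeats the Section 3 rule.
- **Protocol 6.3.2**, which describes the site's call to the IRT, names one single-cohort case, whose arms are those in the VAY736 cohort: "If study participants are only eligible for VAY736 Cohort (i.e., meeting exclusion criterion 1), they will be randomized to either active arm or placebo arm". The paragraph then closes the list: "Otherwise, the participants will be randomized to one of four treatment arms of two cohorts".

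Criterion 1 is not the only cohort-specific entry criterion. Exclusion criterion 18 bars women who could become pregnant unless their contraception meets a standard that depends on the cohort. For VAY736 or its placebo the condition is that "they are using highly effective (for Cohort 1". For CFZ533 or its placebo the criterion sets a different standard: "or effective (for Cohort 2 CFZ533/Placebo) methods of contraception during dosing". The required period after stopping also differs: 6 months for Cohort 1 and 14 weeks for Cohort 2.

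**The concern.** Criterion 18 makes a Cohort 2-only patient possible: a woman whose method, or whose committed duration, meets the Cohort 2 requirement and not the Cohort 1 requirement. Section 3 and the SAP keep her in Cohort 2. Section 6.3.2 puts her in the four-arm pool, because she does not meet criterion 1 and the paragraph offers nothing else.

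At stake is entry into a cohort whose own criterion she fails. All Cohort 1 patients who continue receive VAY736 from Week 29, so the placebo arm defers exposure and does not avoid it. Protocol 4.5.1 ties the contraception requirement to an open question about the infant. It notes that "transient peripheral B cell depletion and lymphocytopenia have been reported in infants born to mothers exposed to anti-CD20 antibodies during pregnancy", and says that the duration of any such depletion after exposure to VAY736 in utero is unknown.

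Timing makes a late correction difficult. Randomisation may take place at Baseline, and note 2 to Table 8-1 lets Baseline coincide with Day 1, when the first dose is given. A mismatch could therefore surface on the day dosing is due. The patient would then be either a deviation or a post-randomisation loss from a cohort planned at about 30 per arm (Protocol 12.8.1).

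**Working it through.** The plan gives no figure on this point, so there is none to reproduce. The check sets the rules side by side and then works out the allocation chances.

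**1. What each rule does with each type of patient**

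| Patient eligible for | Section 3 and SAP 1.4 | Section 6.3.2, read literally |
|---|---|---|
| Both cohorts | Four arms | Four arms |
| Cohort 1 only (meets criterion 1) | Cohort 1 arms | Cohort 1 arms |
| Cohort 2 only | Cohort 2 arms | Four arms |

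The rules agree in the first two rows and conflict in the third.

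**2. Whether the third row can be occupied**

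Yes, through criterion 18, by method or by duration. Criterion 18 speaks of use during and after dosing, so a woman who would adopt the Cohort 1 standard if assigned there can be counted as eligible for both cohorts. That makes the group smaller but does not empty it.

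**3. Chance of Cohort 1 for a Cohort 2-only patient**

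Inputs: the 1:1:1:1 ratio (Section 3), two of the four arms in Cohort 1, and open-label VAY736 for all of Cohort 1 from Week 29 (Section 3).

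- Literal 6.3.2, fixed 1:1:1:1 within the four-arm pool: 2/4 = 50% for Cohort 1, and 1/4 = 25% for active VAY736 in the blinded phase. The chance of VAY736 by the start of open-label treatment is 50%, if she continues.
- Section 3 and SAP 1.4: 0%.

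**4. If the IRT instead rebalances the whole trial to 1:1:1:1**

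Let *s* be the share of all patients who are Cohort 1-only. Cohort 1 is to hold half the trial, so the four-arm pool (share 1 − *s*) supplies the remaining 0.5 − *s*:

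P(Cohort 1 | four-arm pool) = (0.5 − *s*)/(1 − *s*)

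The documents do not give *s*. The values below are assumptions.

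| *s* | Calculation | P(Cohort 1) |
|---|---|---|
| 0 | 0.5/1.0 | 50% |
| 0.1 | 0.4/0.9 | 44% |
| 0.2 | 0.3/0.8 | 37.5% |
| 0.3 | 0.2/0.7 | 29% |

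So 50% is an upper bound. Over this range of *s* the literal reading gives 29% to 50%, against 0%.

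**5. Number of patients**

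A count needs the share of participants who are women of child-bearing potential and the share of those who meet only the Cohort 2 standard. Protocol 1.1.1 says that about 90% of lupus patients are women, with onset typically in the childbearing years. Neither share is given, so no count can be derived.

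**The case against.** The strongest reply is that the design is right and one paragraph fails to repeat it. That much stands: the Cohort 2-only branch exists in Section 3 and in SAP 1.4, so a reader who concludes that the plan has no such branch goes too far. The fault lies in 6.3.2 and in its conflict with the other two texts.

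The second reply is that safeguards prevent any harm. Section 6.3.2 has the investigator confirm all entry criteria before contacting the IRT, and Section 5 bars anyone who deviates from any of them. Section 4.5 keeps out women whose adherence to contraception is in doubt, and Section 7 requires their agreement at consent. These help, but they do not settle the matter, because for a four-arm patient the cohort is unknown until the IRT assigns it. If confirming all criteria means meeting both cohorts' standards, the lower Cohort 2 standard never decides anyone's entry, and the VAY736-only branch of 6.3.2 has no one in it. If it means meeting at least one cohort's standards, 6.3.2 sends the Cohort 2-only woman to four arms. Either way the texts conflict, and nothing readable says how eligibility for each cohort is recorded before the call.

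The third reply is that misallocation is only inferred. This stands. A reader might infer that women were in fact sent to VAY736 against criterion 18. The documents do not support that, because the IRT specification is not among them, the system may have been built to Section 3, and text directly after criterion 18 is redacted.

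A reader might also add hepatitis B as a second large source. In Section 8.4.4 a HepBc Ab-positive patient in Cohort 1 needs "prophylactic anti-viral treatment (e.g., lamivudine or entecavir) initiated latest on day 1", whereas Cohort 2 requires monitoring only. But where local guidelines do not recommend prophylaxis, 8.4.4 limits enrolment to HepBc Ab-negative patients, so those patients are outside the study and not Cohort 2-only. What remains is the individual who cannot or will not take prophylaxis. The 20% to 80% prevalence range in Section 4.1 describes antibody positivity and says nothing about how many such individuals there are. Text after criterion 15 is also redacted. This route is at most secondary.

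**Conclusion.** The contradiction is established from the text. Section 6.3.2 treats criterion 1 as the only source of single-cohort eligibility. Section 3 and SAP 1.4 do not, and criterion 18 supplies a group for which the two rules give different allocations. For a patient in that group the chance of Cohort 1 is up to 50% under the literal 6.3.2, lower with overall rebalancing, and 0% under the other two texts.

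The finding does not extend to an actual misallocation or to a number of patients. It also shows no error in the endpoint, the error rates or the sample size: the primary comparison is made within each cohort. The 50% assumes that the IRT follows 6.3.2 as written with equal allocation to the four arms. The lower figures assume both overall rebalancing and a Cohort 1-only share that the documents do not give.

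**What to change.** Rewrite the allocation paragraph of 6.3.2 to agree with Section 3 and SAP 1.4, with three explicit branches: eligible for Cohort 1 only, for Cohort 2 only, or for both. State that eligibility for each cohort is recorded as yes or no before the IRT call, against every cohort-specific criterion (criterion 1, criterion 18 and the hepatitis B conditions in 8.4.4). The IRT should randomise within the cohort when only one answer is yes.

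Enrolment appears complete: SAP 1.4 applies protocol amendment 5 to the last three patients only, and SAP Section 5 says that the final Cohort 2 results are already reported. For this study the useful step is therefore to compare the IRT specification as built with the two rules and to check past Cohort 1 allocations against the cohort-specific criteria. Any mismatch should be reported as an eligibility deviation.

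The cost is one paragraph, one eligibility entry and one retrospective check. The downside of the third branch is that cohort sizes may drift slightly from 1:1, which the VAY736-only branch already allows. No view is taken on which contraception or prophylaxis rule is right. The sponsor must reconcile those passages.
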